### **Description of Procedures Being Performed**

Description of Phenotypic Measures (See Table 3):

The phenotypic measures include standardized measures such as history and physical, neurologic exam, treatment history, prenatal-perinatal questionnaire as well as the measures listed below.

Vineland Adaptive Behavior Scale (VABS): The VABS is a semi-structured interview designed to measure personal and social sufficiency in individuals from birth to adulthood. It provides a general assessment of adaptive behavior within the sub-domains of Communication, Daily Living Skills, Socialization, and Motor Skills. Administration takes between 20-60 minutes.

Description of Outcome Measures:

Parent-Rated Measures

The Aberrant Behavior Checklist (Aman et al., 1985) is a caregiver report symptom checklist validated and widely used for assessing problem behaviors in children and adults with intellectual disability. Fifty-eight specific items are rated and a manual provides comprehensive descriptions for each assessed behavior. The 58 items resolve into five subscales: Irritability; Lethargy/Social Withdrawal; Stereotypic Behavior; Hyperactivity; Inappropriate Speech.

The Repetitive Behavior Scale-Revised (Lam and Aman, 2007) is a validated tool that captures the breadth of restricted and repetitive behaviors in ASD. The RBS-R has 43 items that resolve into five factors and a total score: Ritualistic/Sameness; Stereotypies; Self Injury; Compulsive Behavior; Restricted Interests. The RBS-R is a continuous measure of the presence and severity of repetitive behaviors. A total score is generated, with higher scores indicating more restricted, repetitive and stereotyped behaviors but each subscale independently shows adequate psychometric properties and acceptable reliability and validity.

The Sensory Profile (Dunn, 1999) is a caregiver questionnaire which measures responses to sensory experiences in everyday life. There are 125 items in the full Sensory Profile, and there is a short version which contains 38 items commonly used in research settings. Sensory processing subscales on the Short Sensory Profile (SSP) include tactile sensitivity, taste/smell sensitivity, visual/ auditory sensitivity, movement sensitivity, low energy/ weak, and under-responsivity/seeks sensation. Tactile, smell/taste and visual/auditory sensitivity scores represent a child's ability to respond to respective sensory stimuli in the environment. Parents use a Likert scale to rate how frequently their child demonstrates a particular behavior (ranging from 1 = always to 5 = never). A lower score indicates greater deviation from typically developing children and indicates more sensory reactivity symptoms.

The Caregiver Top Three Concerns is a Visual Analog Scale rating of severity of the top three causes for concern for the caregivers. Caregivers are instructed to identify causes for concern that are related to the individual's PMS.

Clinician-Rated Measures

The PMS Domain Specific Concerns is a Visual Analog Scales that assesses domain specific individualized items that are identified as key areas of impairment by caregivers. The domains that are assessed are: Social Withdrawal, Repetitive Behaviors, Speech and Language, Anxiety, Motor Performance, Sensory Reactivity, and Cognition. The identified concerns should be related to the subject's PMS.

The Clinical Global Impression – Severity of Illness (CGI-S) and Clinical Global Impression – Improvement of Illness (CGI-I; Guy, 1976) are brief, easy to administer, clinician-rated measures. The CGI-S asks the clinician to rate the patient's current severity of illness based on the clinician's clinical experience with the relevant population. The CGI-S is rated on a 7-point scale, with a range of responses from 1 (normal, not at all ill) through 7 (amongst the most extremely ill patients). The CGI-I asks the clinician to rate the patients' total improvement since baseline, whether or not the improvement is judged to be due entirely to the experimental treatment. The CGI-I is rated on a 7-point

scale, with a range of responses from 1 (very much improved) to 7 (very much worse). For both the CGI-S and the CGI-I, the clinician is allowed to use all available information at the time of the rating. The CGI-I has emerged as a convention for bifurcating clinical trial subjects into "responders" (i.e. a CGI-I of 1 or 2) and "non-responders" (i.e. a CGI-I of 3 to 7) (Busner et al., 2009). In this application, the CGI-I can be a useful tool for gaining a general overview of the therapeutic potential of an experimental treatment. We will improve the sensitivity of the CGI-S and –I by using anchor points that are specific to the signs and symptoms of FXTAS and train all sites in the application.

**Peabody Picture Vocabulary Test (PPVT):** This is a wide-range measure of receptive language for standard English that is administered by a clinician to children in the 2-6 age range. It takes 10-15 minutes to administer.

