#### **Background**

In recent years there have been major changes in the understanding of the etiology of autism spectrum disorders (ASD) and many genes associated with ASD have been identified. This has led to a profound shift in thinking, such that ASD can now be conceived of as having multiple independent causes, which in many cases can be largely attributed to a specific etiological genetic event. One such example is the 22q13 deletion syndrome, also called Phelan-McDermid syndrome (PMS), characterized by global developmental delay, hypotonia, delayed or absent speech, and ASD features, for which convincing evidence implicates SHANK3 as the critical gene (Bonaglia et al, 2006). SHANK3 codes for a master scaffolding protein which forms the framework in glutamatergic synapses (Boeckers et al, 2006) and makes up the core of the postsynaptic density (PSD). Recent studies exploring the rate of 22q13 deletions/SHANK3 mutations suggest that haploinsufficiency of SHANK3 can cause a monogenic form of ASD and intellectual disability with a frequency of up to 2% of ASD cases (Durand et al, 2007; Moessner et al, 2007; Gauthier et al, 2008; LeBlond et al., 2015). Although SHANK3 mutations and deletions account for a relatively small proportion of ASD cases, recent evidence suggests that this variant may be treatable, and therefore important to identify.

Work on PMS at our Center began with Shank3-deficient mice showing a reduction in basal neurotransmission reflecting decreased glutamate (i.e., AMPA receptor-mediated) transmission. Long-term potentiation was impaired with no significant change in long-term depression (Bozdagi et al., 2010), and intraperitoneal injection of IGF-1 reversed the electrophysiological and motor deficits seen in the Shank3-deficient mice (Bozdagi et al., 2013).

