## **8. Subjects - Populations**

### **Inclusion Criteria**

Diagnosis: Pathogenic deletions or mutations of the SHANK3 gene confirmed by array CGH and/or direct sequencing.

Age Range: Cases will be between 2 and 12 years old at the time the phenotypic measures were collected.

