### **How Participants Will Be Identified**

All participants must be diagnosed with Phelan McDermid Syndrome.

Phenotype definition will be conducted using a comprehensive assessment battery, including: (1) psychiatric evaluation; (2) clinical genetics evaluation; (3) neurological examination; (4) Vineland Adaptive Behavior Scales.

All patients must also have pathogenic deletions or mutations of the SHANK3 gene confirmed by array CGH and/or direct sequencing on record.

**Who Will Initially Approach Potential Participants** Study Personnel, Member of Primary Care Team, Treating Physician, Clinic Personnel

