Auditory Event Related Potentials (AERPs) are useful for characterizing early processing of auditory tones and habituation to rapidly repeated stimuli as in speech processing. Tones are presented in rapid succession (e.g., up to every 500 ms) and ERP components to both initial stimulus presentations and their habituation to subsequent stimuli (i.e., reduction in amplitude) are examined. Auditory gating waveforms have been well characterized across development (Milner et al., 2014; Tremblay et al., 2014; Magnee et al., 2011) and are comprised of a fronto-central peak 100 ms after the onset of the auditory stimulus (N1) and a subsequent positive peak (P2) reflecting activity in auditory cortex, mesencephalic reticular activating system, planum temporale, and auditory association cortex (Crowley et al., 2004; Godey et al., 2001). The N1-P2 complex reflects two distinct components: initial stimulus processing (N1) and subsequent attention to and processing of stimulus information (P2). P2 also has been implicated in speech processing (Knowland et al., 2014; Klucharev et al., 2003) suggesting that its analysis may be important for understanding neurophysiological mechanisms associated with broader cognitive and language developmental dysfunctions in FXTAS. Recent AERP studies suggest that measures of auditory gating may provide a sensitive and selective probe of sensory physiology in FXTAS (Hall et al., 2009). Individuals with FXTAS, for example, show auditory hypersensitivities consistent with Fmr1KO mouse models of local-circuit hyper-excitability involving prolonged "UP" states in the gamma frequency range, decreased glutamatergic drive on fast-spiking GABAergic inhibitory neurons in sensory cortex, and heightened neurophysiological response to auditory stimuli (Rotschafer et al., 2013).

The Sensory Assessment for Neurodevelopmental Disorders (SAND) is a clinician-administered assessment and corresponding caregiver interview that is not dependent on verbal or cognitive ability and is therefore appropriate for severely affected or nonverbal individuals with FXTAS. The algorithm measures sensory discrete hyperreactivity, hyporeactivity, and seeking behaviors across visual, tactile, and auditory domains. The SAND has also been validated in ASD with significant correlation to the previously validated Sensory Profile. Results from our preliminary data suggest the SAND can identify sensory reactivity subtypes that differentiate FXTAS and other forms of ASD.

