Justification for Meeting Criteria	
Growth hormone is FDA approved for use in children with growth hormone deficiency (including idiopathic [of unknown cause] growth hormone deficiency), Turner syndrome, Noonan syndrome, Prader-Willi syndrome, short stature homeobox-containing gene (SHOX) deficiency, chronic renal insufficiency, idiopathic short stature and children small for gestational age. (https://www.fda.gov/Drugs/DrugSafety/ucm237839.htm) This research is intended as a pilot clinical trial to look at social withdrawal and repetitive behavior in children with PMS and not as a new indication for GH treatment. Our study population will not have growth hormone administered for any of the FDA approved indications. The results of this study may warrant further such studies in the future. The dose of daily growth hormone varies with the indication for therapy. Approved doses of growth hormone range from 0.16-0.25mg/kg/week for growth hormone deficient patients (Grimberg et al.; 2016) and up to 0.47 mg/kg/week for patients born small for gestational age. In our proposed trial, we expect a majority of our patients to be growth hormone sufficient and therefore similar to the population of children with idiopathic short stature treated with growth hormone. We will recommend a dose of 0.15mg/kg/week divided daily for 2 weeks as a starting dose to ensure safety and tolerance. The dose will then be increased to 0.3mg/kg/week for 10 weeks, an average growth hormone dose in children with idiopathic short stature. We will obtain an exemption from the FDA IND for the use of growth hormone in this study. Neither the patients nor their insurances will be charged for growth hormone. The medication will be funded by the study and provided to families to administer daily at home.

To be a coordinating center, the Mount Sinai investigator is the Principal Investigator for multi-site participation in the trial. The Investigational Drug Service (IDS) may support trials as the coordinating center. IDS services include but are not limited to randomizing for other sites, storing and shipping drugs to participating sites, etc.

Icahn School of Medicine at Mount Sinai (ISMMS) Is the Coordinating Center	Yes
Role of the Investigational Drug Service (IDS)	Not applicable, single center study

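### As written, the CGI-S and CGI-I are to be scored with anchor points for FXTAS, a condition that no child in this Phelan-McDermid trial is required to have

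*Combined protocol and SAP*

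**What the plan says.** Section 12 (Description of Procedures Being Performed) lists the CGI-S and CGI-I among the clinician-rated outcome measures. It describes both as 7-point scales. The CGI-S is rated from the clinician's experience with the relevant population, and the CGI-I rates total improvement since baseline. On responder status it observes: "The CGI-I has emerged as a convention for bifurcating clinical trial subjects", with scores of 1 or 2 on one side and 3 to 7 on the other. The description closes with an undertaking to raise the sensitivity of both scales by using "anchor points that are specific to the signs and symptoms of FXTAS and train all sites in the application".

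The population is defined differently. The Inclusion Criteria in section 8 require "Pathogenic deletions or mutations of the SHANK3 gene confirmed by array CGH and/or direct sequencing", and section 9 states: "All participants must be diagnosed with Phelan McDermid Syndrome". On the number of centres, section 7 answers no to the multi-center question, and section 25 gives the role of the Investigational Drug Service as "Not applicable, single center study".

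**The concern.** The closing sentence on the CGI is an instruction, not background. It says how two scales will be scored and who will be trained to score them. Anchor points tell a rater which signs correspond to which score. If they describe a different condition, the rater has no sound basis for placing a child with PMS on the severity scale, or for judging which changes count as improvement. The stated reason for having anchors, better sensitivity, would then be lost.

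The CGI-S and CGI-I are the only global clinician ratings among the listed measures, in an open-label, single-group trial whose primary outcome is a caregiver report. A reader of the results would want to know what the global scores were anchored to.

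**Working it through.** No arithmetic applies. The point concerns the content of a measure and depends on no sample size, power or error rate. The check is a comparison of sections.

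1. **Is FXTAS the trial's condition under another name?** The documents never define the abbreviation, but they separate the two conditions. The Objective Measures text says: "Individuals with FXTAS, for example, show auditory hypersensitivities consistent with Fmr1KO mouse models of local-circuit hyper-excitability". The Background, writing of PMS, says that "convincing evidence implicates SHANK3 as the critical gene". One is linked to an Fmr1 model and the other to SHANK3. FXTAS appears in no eligibility criterion.

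2. **How often does FXTAS occur, and where?** It occurs six times: once in the CGI text and five times under Objective Measures, in the descriptions of the auditory potentials and the SAND. One of those five describes the SAND as "appropriate for severely affected or nonverbal individuals with FXTAS". These five are rationale. Only the CGI mention governs how a score is produced.

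3. **Does another section supply the right anchors?** Section 14 lists the CGI-S and CGI-I by name and does not mention anchors. No section available for review gives PMS-specific CGI anchors.

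4. **Is the CGI text consistent with itself?** It is not. The CGI-S is to be rated from experience with the relevant population, which here is children with PMS, while the anchors are for FXTAS. The two neighbouring scales, Caregiver Top Three Concerns and PMS Domain Specific Concerns, are both tied explicitly to PMS.

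5. **Are there several sites to train?** Section 6 assigns all 20 children to one site, and sections 7 and 25 describe a single-centre study. Section 25 also marks the institution as a coordinating center, but no second site is listed for enrollment.

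6. **What depends on the CGI?** It is absent from the objectives and from the endpoint list in section 3. The data analysis plan in section 21 does not name it. The responder split is reported as a convention that can give a general overview. It is not set up as an endpoint, and no responder rate is planned.

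**The case against.** The strongest reply is that this is leftover text. Training several sites makes no sense in a single-centre study, and the same foreign abbreviation recurs in the next part of the section. The Background reports that the group has evaluated patients with PMS since 2010, 65 of them at this site. Such a team is unlikely to rate these children against another condition's signs. The Research Plan PDF listed under Attachments is not available here and may already contain suitable anchors. This stands as an account of what was probably intended, and it rules out saying that the ratings will in fact be mis-anchored. It does not remove the error, because a rater working from these documents has no other anchor instruction. Ignoring the sentence would leave the anchors unspecified.

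The second reply concerns importance, and it stands. The plan has other measures that do not rest on caregiver report alone: the clinician-rated PMS Domain Specific Concerns, the clinician-administered SAND, visual and auditory potentials, and eye tracking. The CGI rater is also unblinded and may use all available information, so correct anchors would not make the CGI an independent check on caregiver report.

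A reader might also infer that wrong anchors would shift a responder rate by a stated number of percentage points. The documents do not support this. They give no misclassification rate and plan no responder analysis. The CGI-I compares each child with their own baseline, so unsuitable anchors need not change responder status at any particular rate. Errors in opposite directions would partly cancel.

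**Conclusion.** The anchor instruction for the CGI-S and CGI-I is wrong as written. It names a condition that the eligibility criteria do not require, and it provides for training at multiple sites in a single-centre study. Confidence in the textual error is high. The conclusion rests on two things: the documents' own Fmr1 versus SHANK3 contrast, since FXTAS is never defined, and the absence of any correction in the sections available.

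Severity is low. The primary outcome, the ABC Social Withdrawal subscale, is unaffected. No size can be given in points or patients, and none should be quoted. The stronger conclusion, that the trial's responder findings would be invalid, does not follow, because no such findings are planned.

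**What to change.** In section 12, Clinician-Rated Measures:

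- Replace FXTAS with Phelan-McDermid syndrome in the CGI sentence.
- Identify the PMS-specific CGI anchors before the first rating, by attaching them or by citing the document that holds them. The domains of the PMS Domain Specific Concerns scale are one possible framework. They are not required, and reusing them could make the two scales overlap.
- Replace the multi-site training wording with training of this site's CGI raters.

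In the same edit, correct the five FXTAS mentions under Objective Measures. Check whether the supporting statements there apply to PMS, because a change of abbreviation alone could leave claims that were made about another condition.

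Timing matters because the CGI-I is judged against baseline. Anchors changed after open-label ratings have begun would leave scores made under different rules. The cost is one wording amendment and, if PMS anchors do not already exist, one anchor sheet. No visits or patients are added.

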#### Objective Measures

Visual Evoked Potentials (VEPs) provide a noninvasive technique to evaluate the functional integrity of visual pathways in the brain from the retina to the visual cortex via the optic nerve/optic radiations. The VEP is recorded from the head's surface, over the visual cortex, and is extracted from ongoing EEG through signal averaging. VEPs reflect the sum of excitatory and inhibitory postsynaptic potentials occurring on apical dendrites (Zemon et al., 1986) which modulate excitatory and inhibitory signals received by the pyramidal cells. The major positive and negative peaks and troughs in VEP waveforms reflect different cellular events. The contrast-reversing checkerboard stimulus used in this study produces a positive peak at approximately 60 ms (P0 or P60), reflecting activation of the primary visual cortex from the lateral geniculate nucleus. A negative peak at approximately 75 ms (N0 or N75) reflecting depolarization and glutamatergic postsynaptic activity spreading to the superficial layers of primary visual cortex, and a positive peak at approximately 100 ms (P1 or P100) reflecting superficial hyperpolarization and GABAergic activity (Zemon et al., 1980). VEPs have been used in clinical trials; for example, an antiepileptic drug (gabapentin; Conte et al., 2009) and an infant formula (O'Connor et al., 2001); both received FDA approval based in part on positive findings from VEP studies. Data from ongoing clinical trials at Mount Sinai provide support for use of VEPs as a measure of treatment response.

Auditory Event Related Potentials (AERPs) are useful for characterizing early processing of auditory tones and habituation to rapidly repeated stimuli as in speech processing. Tones are presented in rapid succession (e.g., up to every 500 ms) and ERP components to both initial stimulus presentations and their habituation to subsequent stimuli (i.e., reduction in amplitude) are examined. Auditory gating waveforms have been well characterized across development (Milner et al., 2014; Tremblay et al., 2014; Magnee et al., 2011) and are comprised of a fronto-central peak 100 ms after the onset of the auditory stimulus (N1) and a subsequent positive peak (P2) reflecting activity in auditory cortex, mesencephalic reticular activating system, planum temporale, and auditory association cortex (Crowley et al., 2004; Godey et al., 2001). The N1-P2 complex reflects two distinct components: initial stimulus processing (N1) and subsequent attention to and processing of stimulus information (P2). P2 also has been implicated in speech processing (Knowland et al., 2014; Klucharev et al., 2003) suggesting that its analysis may be important for understanding neurophysiological mechanisms associated with broader cognitive and language developmental dysfunctions in FXTAS. Recent AERP studies suggest that measures of auditory gating may provide a sensitive and selective probe of sensory physiology in FXTAS (Hall et al., 2009). Individuals with FXTAS, for example, show auditory hypersensitivities consistent with Fmr1KO mouse models of local-circuit hyper-excitability involving prolonged "UP" states in the gamma frequency range, decreased glutamatergic drive on fast-spiking GABAergic inhibitory neurons in sensory cortex, and heightened neurophysiological response to auditory stimuli (Rotschafer et al., 2013).

The Sensory Assessment for Neurodevelopmental Disorders (SAND) is a clinician-administered assessment and corresponding caregiver interview that is not dependent on verbal or cognitive ability and is therefore appropriate for severely affected or nonverbal individuals with FXTAS. The algorithm measures sensory discrete hyperreactivity, hyporeactivity, and seeking behaviors across visual, tactile, and auditory domains. The SAND has also been validated in ASD with significant correlation to the previously validated Sensory Profile. Results from our preliminary data suggest the SAND can identify sensory reactivity subtypes that differentiate FXTAS and other forms of ASD.

Eye tracking will utilize three tasks to measure attention in general and social attention specifically. (1) The Visual Paired Comparison task presents two identical stimuli (faces or patterns) side by side for familiarization. The familiar stimulus and a new stimulus are then paired on test and recognition is inferred from preferential looking to the new target. (2) The Gap-Overlap task measures the latencies of gaze shifts from a central fixation point to a peripheral target are under 2 conditions. During gap trials, the fixation cross disappears prior to the onset of the peripheral cue, whereas in the overlap condition, the fixation cross remains on the screen throughout the trial. Saccadic latencies are typically greater for overlap than for gap trials since the former requires disengagement of attention in addition to orienting to a target (gap effect). (3) Flicker measures the temporal resolution of attention. Four squares that flicker from black to white are presented against a grey background. The target square flickers 180 degrees out-of-phase from the three distractors. Flickering occurs at 1 of 4 frequencies: 0.2, 0.5, 1, or 2 Hz. A preference for the target square indicates phase individuation, which is easier at slower frequencies. Participants are required to look at a screen for approximately 10 minutes while images of human faces will be presented and automated assessments of time spent looking at socially salient features of test images are recorded.

